The study is an individually randomized group treatment (IRGT)³⁴ trial such that the individual, in this case the family, is the unit of randomization. It differs from a classic individually randomized trial in that the intervention is either a group intervention or conducted by an agent responsible for implementing the intervention in a defined set of individuals. The PLAN study will evaluate the effectiveness of family based treatment (FBT) delivered by a coach versus usual care (UC) treatment delivered by primary care providers. Both FBT and UC will be delivered in pediatric offices. In PLAN, participants are randomized at the family level and only one eligible child (the index child) is included in the primary outcome analysis. The trial will enroll up to 1284 subjects from 528 randomized families at four sites, each having at least one overweight/obese participating child age 6-12 and at least one participating parent. Since the study

has four sites with three coaches per site, the analysis plan involves a nesting of the coach within the site. Some sites have backup and floating coaches that are involved in delivering FBT to study participants, which will also be accounted for when outcome data is analyzed (**This change was made on 12.4.18 prior to review and approval by the DSMB, DSMB approved protocol addenda on 11.18.19**). While this nesting suggests a classic cluster randomized trial, an IRGT trial is different because the nesting applies only to the intervention group. Since the UC group has no nesting factor in this IRGT trial, a proper analysis must reflect the fact that the FBT group and the UC group must use different covariance structures. In addition to one participating child and parent from each family, the sample will also include up to 228 overweight/obese siblings and non-participating parents who will not be direct recipients of the intervention. There will be two years of follow-up with comprehensive assessments at baseline, 6, 12, 18 and 24 months. The primary outcome is percent over BMI at 24 months in the child. Our primary hypothesis is that the FBT intervention will be superior to UC alone in the participating child (**DSMB approved protocol addenda, 11.2.18**).

[figure not shown]
Outcome and Objectives

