Additionally, PLAN coaches will be asked to participate in an audio-recorded semi-structured interview; interested coaches will provide consent over the phone and will be asked a series of questions by a trained post-doctoral researcher on the study. The questions are based on the coaches' discussions with FBT families pre-COVID and amid-COVID regarding food cost, perception, and behaviors. The telephone interviews are voluntary and will be completed based on the coaches' availability. (*This change was made 7.13.20, DSMB approval 12.16.2020*)

Randomization

The DCC will use the REDCap randomization module to create an online password protected randomization system that will facilitate the random assignment of families. When the website is entered, the user will provide information that establishes the eligibility of the family. Group assignments will be revealed only if all eligibility criteria are satisfied. To avoid temporal bias, randomization will be blocked within clinic using random block sizes in order to preclude the possibility that investigators might know in advance the assignment of the last family in a particular block.

Families who enroll in the study will be scheduled for a baseline assessment to gather preliminary study data. Following this visit, the family will be randomized and then informed of the treatment condition to which they have been assigned. *A PLAN coach will follow up with families randomized to FBT to schedule the first FBT visit (Session 0; This change was made on 9.18.17 prior to review and approval by the DSMB, DSMB approved protocol addenda on 11.2.18). Ideally, all treatment sessions will take place in the pediatric practices. If there are issues with space at the pediatric practices, FBT families can be seen at alternate locations (i.e., satellite office, university setting, etc.) for their weekly and assessment sessions. Usual care assessments can also be conducted at an alternate setting. (This change was made on 10.17.18 prior to review and approval by the DSMB, DSMB approved protocol addenda on 11.2.18)*

Participant randomization will begin November 2017 (*This change was made on 11.9.2017 prior to review and approval by the DSMB, DSMB approved protocol addenda, 11.2.18*) and will go through August 15th, 2019 (*This change was made on 6.6.19 prior to review and approval by the DSMB, DSMB approved protocol addenda on 9.29.19*).

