Family Demographics	Questionnaire	10	P, P _c	X				
Family Nutrition and Physical Activity (DSMB approved protocol addenda, 9.29.19).	Questionnaire	10	P	X		X		X
Participant Adherence to FBT	Session Attendance ¹	NA	P,C	X	X	X	X	X
Participant Acceptability	Client Satisfaction Questionnaire	5	P,C					X
24 Month Survey (DSMB approved protocol addenda, 9.29.19).	Questionnaire	15	P,C					X
Provider Demographics	Questionnaire	10	PCP	X				
Provider Usual Care Survey	Questionnaire	10	PCP	X				X
Chart review	Questionnaire	--	Plan Coach					X
Coach Demographics (This change was made on 7.25.19 prior to review and approval by the DSMB, DSMB approved protocol addenda on 9.29.19).	Questionnaire	5	PLAN Coach					X
Coach Treatment Knowledge (This change was made on 7.25.19 prior to review and approval by the DSMB, DSMB approved protocol addenda on 9.29.19).	Questionnaire	10	PLAN Coach					X
Coach Attitudes Toward Evidence Based Treatment (This change was made on	Questionnaire	10	PLAN Coach					X

7.25.19 prior to review and approval by the DSMB, DSMB approved protocol addenda on 9.29.19).								
Coach Attributes of FBT (This change was made on 7.25.19 prior to review and approval by the DSMB, DSMB approved protocol addenda on 9.29.19).	Questionnaire	5	PLAN Coach					X
Total Time for Each Group								
Child		12	5	10	5	10		
Parent		55	5	10	5	15		
Provider		25	0	5	0	11		
PLAN Coach (This change was made on 7.25.19 prior to review and approval by the DSMB, DSMB approved protocol addenda on 9.29.19).		0	0	0	0	30		

II. Treatments

Usual Care (UC)

The usual care control group will consist of the care typically delivered by the family's pediatrician for children with overweight or obesity. *(This change was made on 11.9.17 prior to review and approval by the DSMB, DSMB approved protocol addenda on 11.2.18).* The implementation of UC may vary between physicians but typically include an assessment of the child's weight, help removing barriers to weight loss, and introduction of goals for better weight management.

Family-based Behavioral Weight Loss Treatment (FBT)

1. Introduction

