FBT PLAN coaches will be hired by the clinical site PI. Clinical site PIs will be encouraged to hire individuals with at least a bachelor's degree, and who possess, or are pursuing, an advanced degree in a related field of study such as dietetics, social work, or clinical psychology. Basic demographic information will be gathered regarding PLAN coach age, gender, educational background, race/ethnicity, prior experience with families or behavioral health interventions, etc. to help tailor training to their level of experience and to identify any PLAN coach level descriptors associated with ease of acquiring fidelity and competency in intervention delivery. These PLAN coaches will be trained using a combination of education, interactive role-playing, simulations, and treatment practice with pilot patients.

<[name]>

1. Multisite FBT Training

PLAN coaches will attend a multisite FBT training at Washington University in St. Louis during the week of April 24-28, 2017 and at the University at Buffalo on July 11-12, 2017. All PLAN coaches will complete the on-site training workshops and must earn an 80% or above on the post-training assessment at the end of these trainings in order to be certified to initiate recruitment. If any coaches do not achieve this score, remedial instruction will occur and they may repeat the quiz.

2. Educational Materials

The study website will include articles on FBT for the PLAN coaches to read, and it will also provide a thorough training manual to teach behavioral, diet, and exercise principles used in the study, as well as other relevant readings. The website will also include web-based pre- and post-assessments of FBT knowledge. PLAN coaches will need to demonstrate mastery of the material prior to working with families.

3. Interactive Role Playing and Simulation

Live and Skype training sessions will provide the opportunity to role play important behavioral skills. Training will conclude with a treatment session simulation, during which PLAN coaches will be rated on their utilization of FBT components to ensure competency. If the written and simulated assessments demonstrate lack of knowledge and skills, FBT concepts will be retaught until mastery is achieved.

4. Pilot Patients

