With the above comments in mind and with the focus of the study being on a between-group comparison of the change from baseline to 24 months, the primary analysis will be an analysis of covariance with the 24-month value as the dependent variable and with the baseline value as a predictor variable. The statistical model we employ reflects the parametrization described by Baldwin and Colleagues.⁶⁰ It takes the initial form $Y_{24ij} = \beta_{0j} + \beta_{1j}X_{ij} + Y_{0ij} + e_{ij}$. In this model, Y_{24ij} is the 24-month value of the percent over the age and sex matched 50th BMI percentile (the primary outcome) for subject i and cluster j , with the “clusters” being defined by the coach in the intervention group and by individual children in the control group; β_{0j} and $\beta_{1j}X_{ij}$ are the intercept and intervention effect for cluster j ; Y_{0ij} is the baseline value of the outcome measure; and e_{ij} is the normally distributed error term. *In these models, the intercept and baseline are fixed effects while the intervention effect is random (DSMB approved protocol addenda, 11.2.18).* To reflect the partial clustering structure of the IRGT design, the above expression is modified by using the cluster-level equations $\beta_{0j} = \lambda_{00}$ and $\beta_{1j} = \lambda_{10} + \mu_{1j}$ to describe how the coefficients β_{0j} and β_{1j} vary across clusters. *The reparametrization of β_{1j} yields two random effects (DSMB approved protocol addenda, 11.2.18)* and the term μ_{1j} permits between-cluster variability in the outcome measure only within the intervention group (coded as 1). Substituting in the initial equation above yields the final model:

$$Y_{24ij} = \lambda_{00} + \lambda_{10}X_{ij} + \mu_{1j} X_{ij} + Y_{0ij} + e_{ij}$$

Using PROC MIXED in SAS, separate covariance structures will be fit to the FBT group and the UC group to account for the fact that the coach is nested within the site in the FBT group while there is no such nesting in the UC group. All analyses other than the above are secondary or exploratory analyses. One of those secondary analyses will supplement the primary analysis by adjusting for the sex and race of the participating child, family income, the educational level of the participating parent, and whether there are one or two parents in the household. These secondary analyses will provide insight regarding the impact the covariates may have on the primary outcome.

1. Sample Size and Statistical Power

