Table 1 contains the results of the power computations using the parameters discussed above, assuming the compound symmetry covariance structure in both study arms and assuming an intraclass correlation coefficient (ICC) in the UC group of 0.01 and ICCs in the FBT group of 0.04, 0.06, 0.10, and 0.15. We assume a small ICC in the UC group of 0.01 because there is no clustering within that group meaning that the ICC should be essentially zero. While we do not have data with which to estimate the ICC in the FBT group, we note that many cluster trials that involve group interventions have reported ICCs in the 0.01 to 0.05 range. Since the PLAN intervention is individualized and since we expect PLAN children to have no contact with one another, we do not face the impact on the ICC that is present in many cluster trials. This argues for a very small ICC in the FBT group. By contrast, the fact that the same coach will be responsible for multiple children will inevitably increase the ICC above where it might otherwise be. Based on these considerations, we tabulate power for ICCs in the FBT group that range from 0.04 to 0.15. However, the many other studies that have used group interventions while yielding ICCs below 0.05 suggests that the ICC ultimately observed in PLAN will be substantially less than 0.1.

Results in Table 1 indicate that if we recruit 100% of our original target of 528 families, power will be excellent for all tabulated scenarios with an ICC in the FBT group of 0.1 or less. For an ICC

no bigger than 0.1, power remains adequate for most scenarios if we recruit at least 80% of the target (N = 432). If recruitment is below the 80% figure, an adequate power of at least 0.8 requires either the smaller of the two tabulated standard deviations or a mean difference that is at least 60% of the value observed in [name] studies (difference at least 6.4).

Table 1: Statistical power for two sided tests at the 0.05 level of significance.

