Secondary analyses involving the child will look more comprehensively at the pattern of change over time. While there is no specific literature on the use of mixed model repeated measures analyses in IRGT trials, these analyses are known to inflate the type I error in cluster trials⁷⁰ and it is likely that this also occurs in IRGT trials. The general recommendation is therefore that random coefficient models that may use different covariance structures in the two study arms should be employed in the longitudinal analysis of IRGT trials.⁷⁰ With that in mind our secondary analysis of child outcome data will apply these models to all data collected at baseline and at 6, 12, 18 and 24 months. In light of the fact that weight changes in intervention studies sometimes occur more quickly at the beginning with a subsequent leveling off at later time points, these analyses will explore non-linear possibilities such as quadratic models. They will also adjust for the same covariates that were listed in the secondary analysis of the primary outcome to understand the impact of the covariates on longitudinal change.

4. Covariance Structures and Missing Data

There are two key considerations that will guide us as we pursue these secondary random coefficient models: (1) the selection of appropriate covariance structures and (2) the handling of missing data.

5. Selection of a Covariance Structure

PROC MIXED in SAS contains many covariance structure options, including the ability to identify covariance structures that are specific to the UC group and the FBT group separately. Our model-selection process for choosing the appropriate covariance structures will reflect several considerations including information criteria; the pattern of change in the correlation between observations as the time between measurements increases; and the *a priori* preference for structures that, all other things being equal, minimize the number of parameters that must be estimated; and whether data collection is equally spaced. *While confirmation will have to await the availability of the final dataset, we anticipate using an unstructured covariance structure in the primary analysis (DSMB approved protocol addenda, 11.2.18).*

6. Missing Data

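### Randomisation is blocked within clinic, but the primary model names no site or clinic effect common to both arms; adding one is a cheap improvement worth about zero power at the only documented ICC

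*Combined protocol and SAP*

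**What the plan says.** Under Randomization, and again under Measures to Minimize Bias (1. Enrollment and Randomization Procedures), the combined protocol and SAP states that "randomization will be blocked within clinic using random block sizes". Under Description of Study Design it adds: "Both FBT and UC will be delivered in pediatric offices". Each clinic therefore contributes families to both arms.

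The final equation in B. Primary Analysis has an intercept, the arm effect, a random coach term that acts only in FBT, the baseline value and an error term. Clusters are described as "being defined by the coach in the intervention group and by individual children in the control group". Site appears only in the sentence on PROC MIXED, where "the coach is nested within the site in the FBT group while there is no such nesting in the UC group".

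The adjusted analysis in B adds child sex and race, family income, parental education and one or two parents in the household. Sensitivity analysis 5 in section E uses the same list. For the longitudinal models (B.3), "They will also adjust for the same covariates that were listed in the secondary analysis of the primary outcome". Section F may add time to final assessment. None of these names site or clinic. Section B.5 leaves confirmation of the primary covariance structure to the final dataset.

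On clustering in the control arm, the power section says: "We assume a small ICC in the UC group of 0.01 because there is no clustering within that group". The Usual Care section says: "The implementation of UC may vary between physicians".

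**The concern.** When randomisation is stratified by clinic, a level difference between clinics or sites that is the same in both arms largely cancels from the treatment contrast. A model without a common stratum term does not use that cancellation. In the printed model the shared difference has two places to go. In FBT it looks like variation between coaches, because coaches sit within sites. In UC it goes into the residual. Both inflate the standard error of a contrast that is in fact more precise.

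What is at stake is power, not validity: the estimate is unbiased and the type I error falls below 5%. Any coach ICC read from the fitted model would also be too high, although the plan does not commit to reporting one.

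**Working it through.** **Inputs.** From the documents: N = 528, 1:1, so 264 per arm; 4 sites x 3 coaches = 12 coaches, 22 FBT families each; two-sided 0.05; weakest row of Table 1 is a difference of 5.3 with SD 15.3; FBT ICC 0.04 to 0.15; UC ICC 0.01. Assumed, because the documents do not give them: the shared site or clinic ICC (0 to 0.05), the number of clinics and the df method.

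**Step 1: the plan's own figure.** SE² = SD²[(1 + 21·ICC)/264 + 1/264]. At ICC 0.04: 234.09 × (1.84 + 1)/264 = 2.518, so SE = 1.587 and 5.3/1.587 = 3.34. Simulating the written model and testing on 8 df gives power 0.842 / 0.786 / 0.682 / 0.577 at FBT ICC 0.04 / 0.06 / 0.10 / 0.15. Table 1 prints 0.84 / 0.80 / 0.69 / 0.57, so the row is reproduced within 2 points. Satterthwaite df give about 0.89 / 0.85 / 0.75 / 0.65. The absolute powers below therefore run above Table 1; read the differences.

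**Step 2: why the standard error is too large.** Let c be the coach ICC, s the shared site ICC and V the total variance in each arm.

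- True variance of the contrast: V[c/12 + (1 - c - s)/264 + (1 - s)/264]. The site effect itself has cancelled.
- Expected printed-model variance, FBT part: V[c + (9/11)s + (1 - c - s)/22]/12. Of the 11 other coaches, 2 share a site, hence 9/11.
- Expected printed-model variance, UC part: V[1 - (65/263)s]/264. Of the 263 other UC children, 65 share a site.

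At c = 0.04 and s = 0.02 the true value is 0.003333 + 0.003561 + 0.003712 = 0.010606 V. The printed model expects (0.04 + 0.016364 + 0.042727)/12 + 0.995057/264 = 0.008258 + 0.003769 = 0.012027 V. The variance ratio is 1.134, so the SE is 6.5% too large. The same arithmetic gives 3.3% at s = 0.01 and 15.9% at s = 0.05.

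**Step 3: effect on power.** Simulation of the weakest row, coach ICC 0.04, REML, separate residual variance by arm, Satterthwaite df:

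| Shared site ICC | Power as printed | Power, site fixed | Type I error as printed |
|---|---|---|---|
| 0 | 0.890 | 0.882 | 0.047 |
| 0.01 | 0.881 | 0.886 | 0.041 |
| 0.02 | 0.869 | 0.887 | 0.038 |
| 0.05 | 0.825 | 0.893 | 0.029 |

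Separate runs differ by a few tenths of a point. In larger runs over coach ICC 0.04 to 0.15, adding site changes power by -0.6 to +0.4 point at s = 0.01 and by +0.7 to +6.7 at 0.02 to 0.05. For coach ICC 0.04 to 0.06 the latter range is +1.9 to +6.7.

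In stronger rows the gain is smaller. For 6.4/15.3, power goes from 0.967 to 0.970 at s = 0.01 and from 0.941 to 0.974 at 0.05. For 5.3/12.7 it goes from 0.968 to 0.970 and from 0.941 to 0.972.

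**Step 4: dependence on df and clinics.** If the df are fixed at 11 as printed and drop to 8 with site in the model, adding site costs 2.5 points at s = 0 (0.865 to 0.840) and about 1 point at 0.01. At 0.02 it gains 0.6 (0.839 to 0.845).

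If the shared differences lie between clinics, the printed model's own power drops by 2.8 to 8.8 points at ICC 0.02 to 0.05 with one clinic per coach, but only 0.8 to 3.0 with three per coach. With site ICC 0.02 plus clinic ICC 0.03, printed against site fixed plus clinic intercept is 0.823 against 0.896 (one clinic per coach) and 0.839 against 0.893 (two per coach).

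**The case against.** The strongest reply is that no harm is documented. The power section treats UC clustering as essentially nil and uses 0.01 as a stand-in. There the gain is about zero and can be slightly negative. Table 1 itself, at 1000 simulations per cell, has a Monte Carlo standard error of √(0.84 × 0.16/1000) = 1.2 points. Variation in usual care between physicians does not show that levels differ equally in both arms after adjustment for baseline. All of this stands, and it is why the larger gains are given only as assumption-dependent.

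The plan may also intend site already. Eight df equals 12 coaches minus 4 sites, so the simulated model may have contained site, and B.5 does not rule out a common term. That is possible, but no passage says so.

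Three stronger readings are tempting and not supported.

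- A reader might infer that the primary test is invalid or its type I error inflated. For shared level differences the opposite holds.
- A reader might take the nesting sentence to mean a site random effect in FBT only, which would cost far more power. The printed equation has no such term and Table 1 does not fit that reading.
- Because "FBT PLAN coaches will be hired by the clinical site PI", a reader might turn this into a point about treatment effects that differ by site. That is a separate choice between inference for these four sites and inference beyond them. A common site term does not settle it, and it is not part of this point.

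**Conclusion.** The point holds as a cheap improvement. The randomisation strata are absent from the printed primary model and its adjusted versions, and including them is the more efficient match to the design if strata differ.

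The documents do not support a claim of material power loss. At a shared ICC of 0.01 the effect of adding site is -0.6 to +0.4 point. A gain of about 2 to 7 points requires a shared site ICC of 0.02 to 0.05, coach ICC 0.04 to 0.06, Satterthwaite df and the weakest row together. It is smaller if the df fall from 11 to 8 or if each coach covers several clinics. Even at the least favourable site-level setting with coach ICC 0.04, the printed model keeps power of about 0.83. Confidence in the direction is high. Confidence in the size is limited by the undocumented ICC, number of clinics and df method.

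**What to change.** In B. Primary Analysis, before outcome data are unblinded:

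1. Add site as a fixed effect and clinic as a random intercept, both common to FBT and UC.
2. Keep the coach random effect in FBT only.
3. Specify Satterthwaite or Kenward-Roger df.

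Carry the same terms into the longitudinal child models (B.3) and the parent analysis (Secondary Aim 1). Clinic should be random: fixed terms for 12 clinics would cost about 1 to 2 points at a shared ICC of 0.01.

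The work is a few lines of SAP text and PROC MIXED code. Clinic and site are already recorded for randomisation, and Table 1 can stand.

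There are two downsides. If sites do not differ, the site term costs about 0.4 to 1 point of power with Satterthwaite df, or about 2.5 points if fixed df fall from 11 to 8. If the treatment effect varies by site, type I error for inference beyond these four sites is slightly higher than as printed. At a site-by-treatment ICC of 0.02 it is 0.090 against 0.083 with no shared ICC, and 0.089 against 0.070 with a shared ICC of 0.02. For the average effect in these four sites there is no inflation under either model.
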